9.3 Populations for Analyses

Participants will be older adults with mild cognitive impairments (MCI) or mild to moderate Alzheimer's Disease or related dementias (ADRД) who reside in senior living communities and an adult child who lives at a distance. Dyads will be randomly assigned to one of two treatment conditions (video chat vs. virtual reality). All participants who are enrolled in the study and complete the baseline assessment will be included in the primary analyses regardless of whether they complete all components of the intervention.

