1.2 Schema

Note: Because participation in the intervention required both members of the dyad, if one member chose to withdraw during the intervention phase, the entire dyad was discontinued. However, after the

[figure not shown]
intervention phase was completed, individual members could withdraw independently, allowing the other member to continue participating in post-intervention and follow-up surveys. **Attrition prior to the end of the intervention phase:** 20 dyads + 2 individuals (out of 372 consented) = **42/372**, or **11.3%**. **Total attrition over the course of the trial:** 20 dyads + 12 individuals = **52/372**, or **13.9%**.

Participant retention was monitored throughout the study, and reasons for attrition were recorded. Attrition was categorized into the following predefined groups: (1) **Withdrew consent** (participants voluntarily discontinued for personal reasons, such as time burden or loss of interest); (2) **Adverse events** (participants discontinued due to health or safety reasons – physical or psychological – including withdrawal by the study investigator); (3) **Health-related limitations** unrelated to the intervention that prevented continued participation (e.g., hospitalization, fall, cancer treatment); (4) **Protocol deviations or ineligibility** identified post-randomization (e.g., undisclosed history of seizure); (5) **Partner withdrawal**, where the dyadic nature of the study required discontinuation when a study partner withdrew; (6) **Death** during the study period unrelated to the intervention; and (7) **Lost to follow-up**, where participants became unreachable and did not complete one or more follow-up assessments.

Participants who missed one or more survey assessments but later completed subsequent surveys were classified as having **intermittent missing** data. These cases were not considered lost to follow-up and were retained in all analyses for which valid data were available. Reasons for missed assessments were not always reported but were presumed to reflect temporary nonresponse rather than formal withdrawal or disengagement from the study. In addition, in rare cases, survey data were lost due to administrative or technical errors despite participant completion. These cases were treated as **missing (administrative)** in the relevant analyses.

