1.3 Schedule of Activities

Timeline for the Thrive study

Schedule of Assessments for the Thrive Study

	Screen	Consent	Baseline (T1)	Tech 1 (T2)	Tech 2 (T3)	Tech 3 (T4)	Tech 4 (T5)	Post-study (T6)	1 Mo (T7)	3 Mo (T8)
Eligibility	X									
Randomization		X								
Informed Consent		X								
Demographics		X								
Outcome Evaluations*										
Technology sessions - Positive Engagement (self-report)				X	X	X	X			
Technology sessions - Positive engagement (behavioral coding)				X	X	X	X			
Quality of Life			X	X	X	X	X	X	X	X
Mental Health			X	X	X	X	X	X	X	X
Thriving			X					X	X	X
Loneliness and social connection			X	X	X	X	X	X	X	X
Caregiver Guilt			X	X	X	X	X	X	X	X
Family bonding			X	X	X	X	X	X	X	X

* The outcomes listed above refer to general constructs rather than specific measures. Most outcomes will be measured using more than one self-report and/or behavioral assessment.

2 Introduction

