9.4 Statistical Analyses

9.4.1 General Approach

Primary analyses will be based on an **Intent-to-Treat (ITT)** approach in which all randomized participants will be analyzed according to their assigned treatment group, regardless of completion of the intervention. Primary analyses will be performed on the ITT population using appropriate statistical models to compare treatment groups. Secondary analyses will evaluate additional outcomes and mediation models to explore potential explanatory pathways. Missing data will be handled using appropriate statistical techniques including linear models with maximum likelihood estimation. Additional exploratory analyses may be conducted to explore trends, identify potential moderator variables, and generate hypotheses for future research. These results will be interpreted cautiously. All analyses will be performed using validated statistical software (SPSS, R, and Mplus), and findings will be reported in accordance with CONSORT guidelines and relevant best practices in the field. Where appropriate, adjustments for multiple comparisons will be applied to control for Type I error inflation.

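### Section 9.3 makes completing baseline a condition for the primary analyses, while Section 9.4.1 puts all randomised participants in them; the two sets can differ and should be stated once.

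*Combined protocol and SAP*

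**What the plan says.** Two sections of the combined protocol and SAP say who enters the primary analyses.

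- Section 9.3, Populations for Analyses: "All participants who are enrolled in the study and complete the baseline assessment will be included in the primary analyses". The sentence goes on to say that completing the intervention does not matter. It is the only definition of an analysis set under that heading.
- Section 9.4.1, General Approach: under an ITT approach "all randomized participants will be analyzed according to their assigned treatment group, regardless of completion of the intervention". It adds that the primary analyses are run on the ITT population and sets no baseline condition.

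Three other places bear on whether these definitions coincide.

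- In the Schedule of Activities (1.3), the row "Randomization" is marked in the Consent column, alongside informed consent and one column before Baseline (T1).
- On missing data, Section 9.4.1 says "Missing data will be handled using appropriate statistical techniques including linear models with maximum likelihood estimation".
- The Schema (1.2) says "Participants who missed one or more survey assessments but later completed subsequent surveys were classified as having" intermittent missing data, and then "These cases were not considered lost to follow-up and were retained in all analyses for which valid data were available".

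**The concern.** An analyst looking up the primary population would go to 9.3 and find two conditions: enrolment and a completed baseline. Section 9.4.1 has one condition: randomisation. No text says which section governs. If randomisation comes before T1, the baseline condition in 9.3 is a filter applied after randomisation. Whether someone completes T1 could then depend on health, on interest or on knowing the assigned technology. Removing randomised people on that basis gives up part of the protection of random allocation, which 9.4.1 sets out to keep. The removal would also be unnecessary, because the planned likelihood-based models can use later data from a person whose T1 is missing.

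**Working it through.** The plan states no figure for this point, so the check is mainly a comparison of texts, followed by a count of what one affected person would lose.

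**Step 1. Can a person be randomised without T1?** The Schedule marks randomisation at Consent. Section 10.1.1.2 schedules the baseline survey after the dyad is enrolled. Section 6.1.1 takes the background measures right after written consent and puts them a week before the baseline survey. Section 5.5 (Retention) compresses this, placing consent and the baseline survey together in the first week. No section places randomisation after T1, so such a case is possible.

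**Step 2. Who falls in which set?** Here 9.3 is read as a condition of entry and *baseline assessment* as the T1 questionnaires.

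| Randomised person | Meets 9.3 | Meets 9.4.1 | Effect on a likelihood-based estimate |
|---|---|---|---|
| T1 and later data | yes | yes | none |
| T1 only | yes | yes | none |
| No T1, later data | no | yes | later data used or discarded |
| No T1, no later data | no | yes | none; only the reported denominator changes |

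Only the third row can move an estimate. It is also the type of case that the Schema says is retained: a survey missed, later surveys completed.

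**Step 3. What does one such person lose under 9.3?** This assumes complete data after T1.

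- Section 6.1.2 asks all primary measures at four points: baseline, one week, one month and three months. Loss: 3 of 4 = 75%.
- For constructs that the Schedule lists at every wave from T1 to T8, the loss is 7 of 8 = 87.5%.

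Either way, all of that person's post-baseline data go.

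**Step 4. How large is one person relative to the sample?** The Schema counts 372 consented. If all belong to dyads and all were randomised (an assumption), 372 / 2 = 186 dyads, and one person is 1/186 = 0.54% of residents or of adult children.

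**Step 5. Range for the nominal gap.** The number without T1 is not given. For purely illustrative shares of 372 individuals:

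| Assumed share without T1 | In 9.4.1 set | In 9.3 set | Difference |
|---|---|---|---|
| 0% | 372 | 372 | 0 |
| 1% | 372 | 368 | 4 |
| 2% | 372 | 365 | 7 |
| 5% | 372 | 353 | 19 |

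These differences include people with no later data, so they are upper limits on the third row of Step 2. No shift in the treatment effect is computed, because numbers by arm are not available.

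**The case against.** The strongest reply is that there is no real conflict. Section 9.3 says who is included and never says *only*. Its closing clause disregards intervention completion, which is ITT language, and 9.4.1 then names the ITT population. It is true that 9.3 states no exclusion. But if everyone randomised is in anyway, its baseline condition does no work, and in a section that defines populations a condition of entry is a natural reading.

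A second reply is that *baseline assessment* may not mean T1. Section 8.1 uses the term both for demographic and health measures listed under screening and for the pre-intervention questionnaires. On the first reading the gap shrinks or vanishes. This stands as an ambiguity, but the two sections would still state different conditions.

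A third is that the timing evidence is thin: one mark in a table, with 5.5 putting consent and baseline in one week and 10.1.1.2 sending adult children the consent form and baseline survey together. Missing T1 surveys may also be rare, since 6.4 has residents complete surveys with researchers and gives adult children up to three reminders. This bears on how often the gap occurs, not on whether it can.

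A reader might infer more than the documents support:

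- *Lost surveys.* The Schema reports that "survey data were lost due to administrative or technical errors despite participant completion". Someone whose T1 was lost this way did complete it and so meets 9.3. These cases do not separate the sets.
- *The 3-of-4-session minimum in 4.3.* It cannot define the primary set, because 9.3 and 9.4.1 both disregard intervention completion.
- *Replacement of randomised non-starters in 7.2.* They already fall within the 9.4.1 definition, so this is no further contradiction.
- *Early attrition.* The Schema's "20 dyads + 2 individuals (out of 372 consented") gives 20 × 2 + 2 = 42, and 42/372 = 11.3%. This does not measure the gap: the text does not say how many left before T1, and anyone who left then with no later data adds nothing under either definition.

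**Conclusion.** The point holds as an inconsistency in the definition of the primary population. Sections 9.3 and 9.4.1 state different conditions for the same analyses, and the order in the Schedule lets the resulting sets differ. The documents do not show that they did differ, that anyone was excluded, or that a result would change.

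The effect is confined to randomised people without T1 but with later data. Their number is not given and may be zero. Per person, the loss would be all post-baseline data, and one person is about 0.54% of residents or of adult children.

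The conclusion assumes that 9.3 is followed as a condition of entry, that *baseline assessment* means the T1 questionnaires, and that the Schedule shows the true order. The per-person share also treats the 372 consented as 186 randomised dyads. The inconsistency is worth correcting because it concerns the primary analysis set and costs little to remove, not because a large bias has been shown.

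**What to change.** 1. Reword 9.3 to match 9.4.1: the primary population is all randomised dyads, analysed as assigned.
2. State in 9.4 that the planned maximum likelihood mixed models take T1 as one of the repeated outcomes, so that a missing T1 does not remove a person's later data.
3. If a baseline-completer set is wanted, label it a secondary, modified ITT analysis and say whether *baseline assessment* means the T1 questionnaires or the measures taken at screening and consent.
4. Report by arm, separately for residents and adult children, the numbers randomised, with T1, and with any later data. These counts would show at once whether the two definitions ever differed.

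The cost is a few sentences and one flow table. No extra participants, visits or data are needed.

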9.4 Statistical Analyses

9.4.1 General Approach

Primary analyses will be based on an **Intent-to-Treat (ITT)** approach in which all randomized participants will be analyzed according to their assigned treatment group, regardless of completion of the intervention. Primary analyses will be performed on the ITT population using appropriate statistical models to compare treatment groups. Secondary analyses will evaluate additional outcomes and mediation models to explore potential explanatory pathways. Missing data will be handled using appropriate statistical techniques including linear models with maximum likelihood estimation. Additional exploratory analyses may be conducted to explore trends, identify potential moderator variables, and generate hypotheses for future research. These results will be interpreted cautiously. All analyses will be performed using validated statistical software (SPSS, R, and Mplus), and findings will be reported in accordance with CONSORT guidelines and relevant best practices in the field. Where appropriate, adjustments for multiple comparisons will be applied to control for Type I error inflation.

9.4.2 Analysis of the Primary Endpoint(s)

The longitudinal dataset including survey and observational data will enable both between and within participant tests of the hypotheses outlined. The data collected will have three levels of nestedness: repeated measures over time (Level 1), nested within person (either older adult or adult child; Level 2), nested within intervention group (VR vs. Control; Level 3). For some analyses (e.g., Aim 1 and 2), we would not estimate the dyad together since, for example, we do not have specific hypotheses about how the resident and the adult child will differ from each other over time and because the parent and adult child will complete somewhat different measures. Outcomes related to Aim 1 and Aim2 will be assessed with linear mixed-models and, where appropriate, with multilevel structural equation modeling (ML-SEM). ML-SEM merges traditional multilevel modeling, which can accommodate hierarchical data, with structural equation modeling (SEM) techniques, which can accommodate multiple outcomes and mediators, as well as latent variables. Therefore, the analytic approach for some hypotheses tests (e.g., tests of mediation and tests of dyadic models) will be multilevel structural equation modeling (ML-SEM) in Mplus (or R) to simultaneously estimate a within- and between-person model, accounting for individual change over time and the treatment effect at the between-person level. Using parameter constraints, analyses will examine concurrent differences between VR and control (e.g., at a given time point) as well as sustained gains across VR and control using an approach similar to contrast coding.

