6.1.2 Administration and/or Dosing

All residents will participate in their study sessions and surveys from a private room in their senior living community. All adult children will complete their study sessions and all surveys virtually. Resident-adult child dyads will complete a consent form and three brief background measures (on physical health and social isolation), a baseline survey the week before the technology sessions, followed by 4 virtual reality (VR) or Zoom experiences (described below) once a week for four consecutive weeks, a post-study survey, and then a 1- and 3-month follow-up survey. Each VR/Zoom session will last approximately 30 minutes, but could be longer if participants desire. Surveys will occur immediately after each VR/Zoom session, as well as an interview after the last VR/Zoom session (see the table below). All residents will receive the same surveys and all of the adult children will receive the same surveys (the adult children have slightly different measures, such as caregiver guilt, which residents do not complete). All primary outcome measures will be asked at four key time points (baseline, 1-week post-intervention, 1-month post-intervention, and 3-months post-intervention). The surveys after each technology session will be much briefer, focusing on secondary outcomes including experiences with the technology, affective states, and how they felt about their relationship with their family member while using the technology and during the past week. After the study is completely over, the adult children will be emailed a brief, three-minute commercialization survey that asks them the extent to which they would use the product at home if it were available and how much they would pay for it.

All of the VR/Zoom sessions with the residents will occur in person. All interviews will be audio-taped and the VR/Zoom sessions with the residents will be audio and video-taped. The videotapes will be coded later with human and automated coding to assess residents' bodily and conversational engagement while using the VR. All of the audiotapes will be transcribed. The follow-up interviews will be collected face-to-face with the residents and via the telephone for the adult children. The surveys will be conducted in person with the older adult residents. The adult children will complete all of their surveys online through clicking on a Qualtrics link sent to their email.

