6.3 Measures to Minimize Bias: Randomization and Blinding

Stratified Block Randomization Schedule (created with R “randomizeR” package):

- Strata = 4 (UCSB/Rendever x MCI/Dementia)
- Groups (VR/Zoom) = 2 | Block size = 4 (resulting in 6 possible combinations to draw from)
- Iterations (sequences) = 12 | 12 sequences of 4 = 48 subjects
- Results = 48 subjects per strata (equal allocation to conditions)
- Total N = 48 subjects x 4 strata = **192 dyads**

“A” = VR “B” = Zoom

UCSB – MCI	UCSB – DEMENTIA
[1] "A" "B" "B" "A"	[1] "B" "A" "B" "A"
[2] "A" "B" "A" "B"	[2] "B" "A" "A" "B"
[3] "B" "A" "A" "B"	[3] "B" "A" "B" "A"
[4] "B" "A" "A" "B"	[4] "B" "A" "B" "A"
[5] "B" "A" "A" "B"	[5] "B" "B" "A" "A"
[6] "B" "A" "B" "A"	[6] "B" "A" "B" "A"
[7] "B" "A" "B" "A"	[7] "B" "A" "A" "B"
[8] "A" "B" "A" "B"	[8] "A" "A" "B" "B"
[9] "B" "B" "A" "A"	[9] "B" "A" "B" "A"
[10] "B" "A" "A" "B"	[10] "B" "A" "B" "A"
[11] "A" "A" "B" "B"	[11] "A" "B" "A" "B"
[12] "B" "B" "A" "A"	[12] "A" "A" "B" "B"

RENDEVER – MCI	RENDEVER – DEMENTIA
[1] "B" "B" "A" "A"	[1] "A" "A" "B" "B"
[2] "B" "A" "B" "A"	[2] "A" "B" "B" "A"
[3] "B" "A" "A" "B"	[3] "A" "B" "B" "A"
[4] "A" "B" "A" "B"	[4] "B" "B" "A" "A"
[5] "B" "A" "A" "B"	[5] "B" "A" "B" "A"
[6] "A" "A" "B" "B"	[6] "A" "A" "B" "B"
[7] "B" "A" "B" "A"	[7] "B" "A" "B" "A"
[8] "A" "B" "A" "B"	[8] "A" "A" "B" "B"
[9] "B" "B" "A" "A"	[9] "B" "A" "A" "B"
[10] "B" "B" "A" "A"	[10] "B" "A" "B" "A"
[11] "B" "A" "A" "B"	[11] "B" "A" "A" "B"
[12] "B" "B" "A" "A"	[12] "A" "A" "B" "B"

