9.2 Sample Size Determination

Power analysis approach: The approach to estimating power was to use simulation methods. Using this approach, the hypothesized population model and its associated model parameters are used to randomly generate data for the study, including sampling variability. Data are generated thousands of times, simulating thousands of hypothetical studies, and then summarized to explore how many of the simulated studies contain the parameter of interest. The proportion of time each individual effect is significant across all of the simulations is the power of that effect or the expected number of times one would observe that effect to be significant if an alternative hypothesis was true in the population. This approach is the only way to estimate power in this study because of the complexity of the statistical models needed to estimate the treatment effects, that account for the dyadic relationship (resident-adult child) and the longitudinal repeated measures of the outcomes of interest (7 time points). We used the simulation facilities in Mplus (version 8.3) to estimate the models.

To address the proposed aims, which involve dyadic longitudinal models, some with mediation, the power analysis relied heavily on the Phase 1 pilot data as estimates for effects of interest (including within-group changes in well-being over time, baseline to VR). This helps provide a starting point for the simulated datasets. These models, however, are quite complex and involve model parameters for which the pilot data cannot provide reasonable estimates. For example, the pilot study did not collect data on a control group. To be conservative, the power analysis used conservative estimates of effect sizes for models that included differences between VR and the control group (e.g., $d = 0.2$). To determine power, the analysis focused on power of the treatment impact for a given aim (e.g., the hypothesized increase in

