The planned sample size needed to detect an effect size corresponds to the smallest of these effect sizes as our minimal detectable effect of interest – a conservative strategy that would give us adequate power. Various simulation studies were run, varying sample size, effect size of concurrent differences and longitudinal differences, and other model characteristics related to power (e.g., error variance and variance of the random effects). While the models for each aim vary in their specific effects, there are similarities across them. The moderating effects of cognitive impairment are the most specific effects, which would lend itself to lower power. Thus, these models were used as a lower bound for power in this grant and guided the decision on sample size, because if these ML-SEM models with moderation had sufficient power, we can be confident that our other proposed analyses would be sufficiently powered.

We specified a ML-SEM model that included a random effects regression model. We modeled the moderation by including an interaction term (4 conditions: treatment group x cognitive impairment) on its prediction of the fixed effect of quality of life for the Resident in T2-T5 and T6-T7. Additionally, we estimated concurrent differences across the four conditions, conservatively estimating that the effect was small across time ($d = .2$). Using parameter constraints, power was studied for concurrent differences between VR and control (e.g., at a given time point) as well as sustained gains over time between VR and Control.

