We computed that a sample size of **192 dyads (96 in VR condition, 96 in control)** evenly split between cognitive impairment (**MCI vs. dementia**) will achieve a high level of power (.85) for detecting the minimal expected effect size across the different analytic approaches considered. Assuming an attrition rate of approximately 15% across the 4-month longitudinal study, we calculated a required initial sample size of no less than 181 dyads. Based on this analysis, along with the additional considerations noted above, we selected a slightly higher **initial sample size of 192**. Because data from family dyads is dependent, for most analyses the dyad will be treated as the unit of analysis for assignment to experimental conditions and will be modeled accordingly in all statistical analyses. The results of the simulation study reveal that an effective sample size of 192 dyads will provide high power (85%) for detecting even relatively small effects of the VR condition over control (Zoom), which we conceptualized

to be an effect size of $d=.2$, which affords excellent power for detecting even larger effects, which we anticipate will occur.

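### The primary-endpoint analysis (9.4.2) has no term for the site stratum and does not say how baseline (T1) enters the VR-versus-control contrast; the cost is precision, not validity

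*Combined protocol and SAP*

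**What the plan says.** **Randomisation.** Section 6.3 sets up the blocks with "Strata = 4 (UCSB/Rendever x MCI/Dementia". Section 4.1 makes the resident–adult-child pair the unit assigned.

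**Model.** Section 9.4.2 describes repeated measures within person, with persons "nested within intervention group (VR vs. Control; Level 3". It adds: "For some analyses (e.g., Aim 1 and 2), we would not estimate the dyad together". It then states that "analyses will examine concurrent differences between VR and control (e.g., at a given time point", and that sustained gains will also be examined. Section 9.2 says of the dyad that "for most analyses the dyad will be treated as the unit of analysis for assignment to experimental conditions and will be modeled accordingly in all", where the closing word covers every analysis in the plan.

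**Baseline.** Section 6.1.2 states: "All primary outcome measures will be asked at four key time points (baseline, 1-week post-intervention, 1-month post-intervention, and 3-months post-intervention". Section 9.2 refers to "the longitudinal repeated measures of the outcomes of interest (7 time points", a count that includes T1 under the numbering in 4.1. The power model in 9.2, however, predicts "quality of life for the Resident in T2-T5 and T6-T7", a list without T1. H1a, RQ1 and H2a in 2.1 are all worded as effects measured against baseline.

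**Strata in the models.** Cognitive level is a factor of the 2 x 2 x Time design in 4.1 and of the moderation model in 9.2. Site appears in no model in 4.1, 9.2 or 9.4.

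**The concern.** Two things that an analyst needs in order to write the primary model are missing.

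1. Site was used to balance the arms but is not carried into the analysis. A comparison that ignores a balanced, prognostic stratum leaves explained variation in the error term.
2. The T1 measurement could enter in three ways: as a covariate (or through an equality constraint on baseline means), subtracted from the later value, or not at all in a single-visit contrast. These are different estimators with different standard errors, and 9.4.2 does not choose.

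Listing T1 among the repeated outcomes does not settle the second matter. If arm means are free at T1 and data are complete, the single-visit contrast is the post-only difference, or the change difference if T1 is subtracted.

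At stake is precision in a trial designed around a small effect (d = 0.2). There is also reproducibility: two analysts following 9.4.2 could report different primary contrasts.

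**Working it through.** **The plan's own figures.** 4 strata x 12 blocks x 4 = 192 dyads, so 192/2 = 96 per arm; this reproduces. The power of .85 at d = 0.2 (9.2) can be neither reproduced nor refuted, because the variances, correlations and alpha used in the simulation are not given.

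**Inputs.** n = 96 per arm (9.2). Assumed, because the documents give no values: correlation r between T1 and a later visit of .3, .5 or .7; equal variances at T1 and the later visit; complete data. Results are in SD units, for one visit.

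**Formulas.**
- Post-only: SE = sqrt(2/n)
- Change from T1: SE = sqrt(2 x 2(1 − r)/n)
- T1-adjusted: SE = sqrt(2(1 − r²)/n)

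Example at r = .5: post-only sqrt(2/96) = .144; change sqrt(2/96) = .144; adjusted sqrt(1.5/96) = .125.

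| | r = .3 | r = .5 | r = .7 |
|---|---|---|---|
| Post-only SE | .144 | .144 | .144 |
| Change SE | .171 | .144 | .112 |
| T1-adjusted SE | .138 | .125 | .103 |
| Variance ratio, adjusted/change = (1 + r)/2 | .65 | .75 | .85 |
| Variance ratio, adjusted/post-only = 1 − r² | .91 | .75 | .51 |

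**Unequal variances.** Let k be the ratio of the later SD to the T1 SD. In units of T1 variance, the change score has variance k² + 1 − 2rk and the adjusted contrast k²(1 − r²). The difference is (1 − rk)², which is never negative. So in large samples adjustment is not less precise than change, but the gain can shrink. At r = .7 and k = 1.2, change is 1.44 + 1 − 1.68 = .760 and adjusted is 1.44 x .51 = .734, a ratio of .97. At k = 1/.7 = 1.43 the two tie. Against post-only, the ratio stays 1 − r² whatever k is.

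**Validity.** In simulations of 10,000 null trials with 96 per arm and no stratum effect, all three contrasts rejected in 4.8–5.3% of trials. With residents and adult children modelled separately, rejection was 4.8% at a dyad correlation of .2 and 5.1–5.3% at .5 (20,000 trials). Omitting a balanced stratum that explains a share R² of variance gives a type I error of 2(1 − Φ(1.96/sqrt(1 − R²))). That is 4.8%, 4.4%, 3.9% and 2.8% at assumed R² of .02, .05, .10 and .20, which is conservative.

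**The case against.** **The Level 3 label is harmless.** Largely right. Later in 9.4.2 the treatment effect is placed at the between-person level, so arm is a predictor there. A reader might infer a random arm effect, which would leave the comparison unidentified. No passage plans one.

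**Ignoring the dyad inflates type I error.** A reader might infer this from the missing dyad level and the mixed wording in 9.2. It would be true of a model that pooled both members with no dyad term. The documents do not plan that: 9.4.2 gives reasons for modelling members apart in Aims 1 and 2, and 4.1 promises methods for clustered data.

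**Both stratification factors are missing.** This goes too far. Cognitive level is in the design and in the moderation model; only site is absent throughout.

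**The hypotheses already settle the T1 question.** This is the strongest objection. Framing effects against baseline, with 9.4.2 referring to individual change and sustained gains, makes post-only the least natural reading. The comparison with change (.65/.75/.85) therefore deserves more weight than the one with post-only. But hypothesis wording is not a model term: it fits both a change score and an adjusted contrast, and it stands beside a promise of concurrent differences. The parameter constraints in 9.4.2 are described for contrasts, with no mention of baseline means.

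**The absolute SEs are idealised.** True. Section 1.2 reports 372 consented individuals (186 dyads) and 13.9% total attrition, so realised SEs would be larger. With complete data the variance ratios do not depend on n. Sections 1.3 and 6.1.2 also differ on how many visits carry the primary outcomes, which is why the check uses one visit only.

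**Conclusion.** The point holds as an incomplete specification with a precision cost. Site is in no stated model, and the role of T1 in the concurrent contrast is undefined. No planned analysis is shown to be biased or to exceed its nominal error rate.

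If the intended contrast is a change from T1, adjustment would cut its variance by 35%, 25% or 15% at r = .3, .5 or .7. If it is post-only, the cut is 9%, 25% or 49%. These figures rest on assumed correlations, equal variances and complete data; with unequal variances the gain over change may be small. The gain from adding site is not sized, because the documents give no site effect.

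The Level 3 label and the wording on the dyad in 9.2 are minor edits with no numerical consequence for the planned separate models. The specification should be fixed, but it is no ground for doubting the design.

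**What to change.** **In 9.4.2:**
- Add fixed effects for the four site x cognitive-level strata.
- For every primary endpoint measured at T1, estimate all arm contrasts with T1 adjustment by one named method, for example baseline means constrained equal across arms. Exclude the engagement outcomes, which have no T1 (1.3).
- As a minor edit, replace intervention group as Level 3 with the dyad for models that include both members, and make arm a fixed between-dyad effect with visit interactions.

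**In 9.2:** align the conflicting statements about most and all analyses, so that the dyad is modelled in every analysis that includes both members.

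**Dating.** Section 1.2 reports attrition in the past tense, so the edit may follow data collection. Date it. If outcome data by arm had been seen, say so and report the unadjusted contrast beside the adjusted one.

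**Cost:** a few sentences and a few lines of model code. Strata and T1 values are already collected, so no new data are needed.
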